15.3. Institutional Review Board (IRB)/Independent Ethics Committee (IEC)

The Principal Investigator must obtain IRB/IEC approval for the study. Initial IRB/IEC approval, and all materials approved by the IRB/IEC for this study including the subject consent form, written information provided to subjects, and recruitment materials must be maintained by the Principal Investigator and made available for inspection.

16. QUALITY CONTROL AND QUALITY ASSURANCE

16.1. Quality Control

Santen (or designee) will provide instructional material to the study sites, as appropriate; including but not limited to instruction on the protocol, the completion of eCRFs, and study procedures. Santen (or designee) will communicate regularly with site personnel via mail, email, telephone, and/or fax; and make periodic visits to the study site. During those visits, Santen (or designee) will perform source data verification with the subject's medical records and other records relevant to the study. Upon receiving the eCRFs, Santen (or designee) will review and evaluate eCRF data and use standard system edits and may use centralized monitoring to detect errors in data collection.

16.2. Quality Assurance

Santen (or designee) may conduct a quality assurance audit at any time. See [Section 15.2](#).

17. ETHICS

17.1. Ethics Review

The final study protocol and the final version of the informed consent form (ICF), for the main study and the ICF for the pharmacogenomics study, assent form and other study related material, as appropriate, must be approved in writing by an IRB or IEC as appropriate. If an IRB or IEC does not approve the collection of blood samples for optional future pharmacogenomic research, this will not affect the approvals for conducting the main study. The Principal Investigator must submit written IRB or IEC approval to Santen (or designee) before study initiation. Refer to [Section 21.1, Appendix A](#) for a list of obligations of Investigators.

The Principal Investigator is responsible for informing the IRB or IEC of any amendment to the protocol in accordance with local regulations and guidelines. In addition, the IRB or IEC must approve all advertising used to recruit subjects for the study. The protocol must be re-approved by the IRB or IEC upon receipt of amendments.

The Principal Investigator is also responsible for providing the IRB or IEC with progress reports and notifications of any reportable serious adverse drug reactions from the investigational product.

17.2. Ethical Conduct of the Study

This study will be conducted in compliance with IRB or IEC, and regulatory requirements. This study will also be conducted in compliance with the protocol, GCP guidelines, International ICH guidelines, and the Declaration of Helsinki.

17.3. Written Informed Consent

The Principal Investigator at each center will ensure that the subject is given full and adequate oral and written information about the nature, purpose, possible risk and possible benefit of the study and participation in the collection of blood samples for future pharmacogenomic research studies. If the subject does not wish to provide a blood sample for the biomarker research study that it will not affect the subject's enrollment in this clinical trial. Subjects must also be notified that they are free to withdraw from either study at any time. Subjects should be given the opportunity to ask questions and allowed time to consider the information provided. Before participating in any study-related activity, voluntary informed consent must be documented by the use of a written ICF approved by the IRB or IEC and signed and dated by the subject or the subject's legally authorized representative at the time of consent. The original signed and dated ICF will be retained with the study records, and a copy of the signed ICF will be given to the subject or the subject's legally authorized representative. See [Section 21.2, Appendix B](#).

For the pediatric subjects, written informed consent must be signed in accordance with local regulatory and legal requirements by the patient or parent/legal guardian, and giving of assent by the patient if appropriate, must be documented prior to initiation of any study-related procedures. Subjects and their parents/legal guardians must be provided with adequate time to think over their possible participation in the study, to ask questions from the investigator and/or to discuss the study participation with their family or primary care

physician. No measures whatsoever described in the study protocol shall be undertaken, nor any current medication discontinued without such consent indicating that the patient and/or the parent/legal guardian have been given both verbal and written information about the study and the study treatment. The evaluation of whether or not a child can give assent should not solely be based on chronological age, but should also depend on factors such as developmental stage, intellectual capacities and disease experience/understanding.

18. DATA HANDLING AND RECORDKEEPING

18.1. Inspection of Records

The Principal Investigator will allow Santen (or designee), the governing IRB or IEC and applicable regulatory agencies to inspect any aspect of the study, including all study records, eCRFs, and corresponding portions of the subject's charts and medical records at any time during the study. The purpose of these inspections is to verify adherence to the protocol, completeness and accuracy of the eCRF data, and compliance with ICH-GCP guidelines and applicable regulatory requirements.

18.2. Retention of Records

All records relating to the conduct of this study are to be retained by the Principal Investigator until notified by Santen (or designee) that the records may be destroyed.

18.2.1. Source Documents

The Principal Investigator must maintain detailed source documents on all study subjects who provide informed consent. Source documents include subject medical records, hospital charts, clinic charts, medication dosing diaries, study files, as well as the results of diagnostic tests (e.g., visual field test printouts).

The following minimum information should be entered into the subject's medical record:

- The date the subject entered the study and the subject number
- The study protocol number and the name of Santen
- The date that informed consent was obtained
- Evidence that the subject meets study eligibility requirements (e.g., medical history, study procedures and/or evaluations)
- The dates of all study-related subject visits (scheduled and unscheduled)
- Evidence that required procedures and/or evaluations were completed
- Use of any concomitant medications
- Documentation of study medication accountability
- Occurrence and status of any AEs
- The date the subject exited the study and a notation as to whether the subject completed or terminated early from the study, including the reason for early termination
- If unmasking at the site occurred, proper documentation and notifications were made

18.2.2. Source Data

Source data is defined as all information in original records and certified copies of original records of clinical findings, observations, or other activities in a clinical trial necessary for the reconstruction and evaluation of the trial. Source data should be accurate, legible, contemporaneous, original, attributable, complete and consistent. Source data is documented in source documents which may be both electronic and on paper.

The Investigator(s) should be aware about the location of the source data and consistent in recording them. The intended location should be clearly defined prior to subject enrollment. One way of achieving this is to generate a source data location list. The source data location list will be prepared by the site and will be signed and dated by the Principal Investigator. The list will be filed in the Investigator's trial master file.

18.2.3. Data Collection

The Principal Investigator must maintain detailed records on all subjects who provide informed consent. Data for screened and randomized subjects will be entered into eCRFs. eCRFs should be completed within 3 business days of each subject visit as much as possible. Review of the eCRFs will be completed remotely by Santen (or designee). At designated intervals, a study monitor will perform Source Data Verification on site. During those visits, Santen (or designee) will monitor the subject data recorded in the eCRF against source documents at the study site. Santen (or designee) will review and evaluate eCRF data and use standard system edits, and may use centralized monitoring evaluations, to detect errors in data collection. At the end of the study, a copy of the completed eCRFs will be sent to the site to be maintained as study records.

19. PUBLICATION POLICY

The existence of this clinical study is confidential, and it should not be discussed with persons outside of the study. Additionally, the information in this document and regarding this study contains trade secrets and commercially sensitive information that is confidential and may not be disclosed unless such disclosure is required by federal or state law or regulations. Subject to the foregoing, this information may be disclosed only to those persons involved in the study who have a need to know, but all such persons must be instructed not to further disseminate this information to others. These restrictions of disclosure will apply equally to all future information supplied that is indicated as confidential. Information pertaining to this study will be published on www.clinicaltrials.gov.

The data generated by this clinical study are the property of Santen and should not be disclosed without the prior written permission of Santen. These data may be used by Santen now and in the future for presentation or publication at Santen's discretion or for submission to governmental regulatory agencies. Santen reserves the right of prior review of any publication or presentation of data from this study.

In signing this protocol, the Principal Investigator agrees to the release of the data from this study, and acknowledges the above publication policy.

21. APPENDICES

21.1. Appendix A - Obligations of Investigators

In summary, the Principal Investigator has agreed to the following obligations:

- Obtaining informed consent from every subject before the subject's participation in any study-related activity and maintaining records of consent as part of the study records.
- Obtaining approval from the IRB or IEC before involving any subject in any study-related activity; submitting verification of the approval to Santen; submitting periodic progress reports (at least annually) and final report to IRB or IEC.
- Approving the protocol and conducting the study according to the protocol and applicable regulations; informing Santen of all deviations from the protocol.
- Informing the IRB or IEC of all protocol amendments/modifications; sending Santen a copy of the letter from the IRB or IEC approving the amendment/modification.
- Reporting to Santen any AEs and reporting to the IRB or IEC any reportable AEs that occur in the course of the investigation.
- Keeping careful and accurate records of all clinical study data (study records must be considerably more exact and complete than those kept in ordinary medical practice); maintaining records of all materials submitted to the IRB or IEC and of all action by the IRB or IEC regarding the study.
- Making study records available for inspection by Santen and representatives of regulatory agencies and the IRB or IEC; keeping records until notified by Santen that they may be destroyed.
- Maintaining proper control and documentation of all test and control articles.
- Submitting the following records and reporting to Santen. See I, II, and III as listed below.

- I. Before the Beginning of the Study Providing Santen the following:
 - A signed Form FDA 1572, Statement of Investigator, if applicable.
 - A signed Financial Disclosure Form.
 - A current Curriculum Vitae (CV) if not submitted to Santen previously or if updated.
 - CVs for all Sub-Investigators.
 - A letter from the IRB or IEC indicating that the protocol was approved, including the name and address of the IRB or IEC.
 - A copy of the consent form approved by the IRB or IEC.
 - A list of current members of the IRB or IEC.

- A copy of the source data location list.
- A copy of delegation list/log.
- A copy of training log.

II. While the Study is in Progress

- Acknowledgment of receipt of the test and control articles; documentation of disposition of all test and control articles.
- eCRFs for each subject enrolled in the study.
- Information regarding all deviations from the protocol.
- Information regarding all AEs occurring to a subject while enrolled in the study.
- Annual progress report (if study is on-going for more than one year). Letter from the IRB or IEC indicating approval of the annual progress report.

III. Once the Study is Completed

- Disposition of all used and/or unused test and control articles, as well as documentation of all drug accountability.
- Providing Santen a final study report.

21.2. Appendix B - Elements of Informed Consent

I. Elements of Informed Consent

The following information must be provided to each subject in obtaining informed consent as required by ICH-GCP and/or local regulations. If written consent is being obtained, the subject (or subject's legal representative) should be provided with a copy of the signed written ICF.

- A. The trial involves research.
- B. The purpose of the trial.
- C. Name of the Investigator (s) and IRB/IEC
- D. The trial treatment(s) and the probability for random assignment to each treatment.
- E. The trial procedures to be followed, including all invasive procedures.
- F. The subject's responsibilities.
- G. Those aspects of the trial that are experimental.
- H. The reasonably foreseeable risks or inconveniences to the subject and, when applicable, to an embryo, fetus, or nursing infant.
- I. The reasonably expected benefits. When there is no intended clinical benefit to the subject, the subject should be made aware of this.
- J. The alternative procedure(s) or course(s) of treatment that may be available to the subject, and their important potential benefits and risks.
- K. The compensation and/or treatment available to the subject in the event of trial-related injury.
- L. The anticipated prorated payment, if any, to the subject for participating in the trial.
- M. The anticipated expenses, if any, to the subject for participating in the trial.
- N. That the subject's participation in the trial is voluntary and that the subject may refuse to participate or withdraw from the trial, at any time, without penalty or loss of benefits to which the subject is otherwise entitled.
- O. That the monitor(s), the auditor(s), the IRB/IEC, and the regulatory authority(ies) will be granted direct access to the subject's original medical records for verification of clinical trial procedures and/or data, without violating the confidentiality of the subject, to the extent permitted by the applicable laws and regulations and that, by signing a written informed consent form, the subject or the subject's legally acceptable representative is authorizing such access.
- P. That records identifying the subject will be kept confidential and, to the extent permitted by the applicable laws and/or regulations, will not be made publicly available. If the results of the trial are published, the subject's identity will remain confidential.

- Q. That the subject or the subject's legally acceptable representative will be informed in a timely manner if information becomes available that may be relevant to the subject's willingness to continue participation in the trial.
- R. The person(s) to contact for further information regarding the trial and the rights of trial subjects, and whom to contact in the event of trial-related injury.
- S. The foreseeable circumstances and/or reasons under which the subject's participation in the trial may be terminated.
- T. The expected duration of the subject's participation in the trial.
- U. The approximate number of subjects involved in the trial.
- V. Clinical trial information has been or will be available on <http://www.clinicaltrials.gov>.

II. Additional Elements of Informed Consent for Optional Future Pharmacogenomics/genomics Laboratory Research Study

The following information must be provided to each subject in obtaining informed consent for the future pharmacogenomics/genomics laboratory research study:

1. The location of storage of their sample.
2. The duration of storage of their sample.
3. What group(s) within Santen will be using their sample in research study.
4. What use restrictions are assigned to their sample.
5. Destruction of their sample if they withdraw prior to its use, and retention of the sample data if they withdraw after its use.

The informed consent requirements in this protocol are not intended to preempt any applicable local laws which require additional information to be disclosed for informed consent to be legally effective.

Nothing in this protocol is intended to limit the authority of a physician to provide emergency medical care to the extent the physician is permitted to do so under applicable local laws.

21.3. Appendix C - Procedures for Assessments

The following descriptions are for adult and pediatric subjects, however specific guidance for pediatric subjects is shown in Section 21.4.

21.3.1. Demographics, Medication/Therapy and Medical History

Demographics including age, sex, race, prostaglandin analogs naïve status, and ethnicity will be obtained through subject interviews at Visit 1 (Screening).

Medications and procedures/therapies will be confirmed through subject interviews during the study.

Following details of prior medication that has been used for glaucoma or OHT within 28 days before the date of Visit 1, or any concomitant medication, must be recorded in the subject's source documents.

- Name of medication, route of administration, treated eye(s) (if applicable), dose, frequency, indication, start date and stop date

Following details of prior procedure/therapy that has been received for glaucoma or OHT within 28 days before the date of Visit 1, or any concomitant procedure/therapy, must be recorded in the subject's source documents.

- Name of procedure/therapy, treated eye(s) (if applicable), indication, start date and stop date

Medical history including all lifetime ocular medical history to the extent possible, non-ocular medical history within 5 years, diagnosis, ocular surgical history, current ocular and systemic conditions will be confirmed through subject interviews at Visit 1 (Screening) to determine if the subject meets eligibility criteria. Primary diagnosis and the affected eye must be recorded in the subject's source documents.

Name of concurrent disease and affected eye(s) (if applicable) will be confirmed at Visit 1 (Screening) and Visit 2 (Baseline), and recorded in the subject's source documents.

21.3.2. Pregnancy Test

A urine pregnancy test will be conducted using a commercially available test kit at Visit 1 (Screening), Visit 2 (Baseline), Visit 5, Visit 6, Visit 7, and Visit 8 Study Exit/Early Termination for all females of childbearing potential. A female is considered of childbearing potential unless she is post-menopausal (at least 12 months since last menses occurred), is without a uterus or without both ovaries, or has had a bilateral tubal ligation. To perform the pregnancy test, follow instructions provided by the manufacturer of the urine pregnancy test kit.

[figure not shown]

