7.4.1. Visit 1 (Screening)

- Explain the purpose and conduct of the study to the subject and obtain written individual informed consent. Informed consent for the optional pharmacogenomics/genomics laboratory research study may be obtained at any visit prior to blood sampling. Ensure the subject understands that if he/she does not wish to provide a blood sample for the pharmacogenomics/genomics laboratory research study that their decision will have no influence on their participation in the main study.

For pediatric subjects, written informed consent must be provided by the parent/legal guardian, and assent should be provided by the pediatric subjects. The evaluation of whether or not a child can give assent should not solely be based on chronological age, but should also depend on factors such as developmental stage, intellectual capacity and disease experience/understanding.

- Prepare the list of screening/registration of subjects.
- Obtain demographics.
- Obtain medications, procedures/therapies and medical history including all lifetime ocular medical history to the extent possible, non-ocular medical history within 5 years, diagnosis, ocular surgical history, current ocular and systemic conditions.
- Obtain urine and perform urine pregnancy test, if the subject is a female of child-bearing potential.

- As per Schedule of Events and Procedures [Table 3](#) (for adult subjects) or [Table 4](#) (for pediatric subjects), perform the following procedures or assessments (all ophthalmic procedures to be performed in both eyes):
 - Vital signs (blood pressure/pulse rate)
 - Refraction
 - BCVA (before IOP measurement)
 - Biomicroscopy (before IOP measurement)
 - IOP
 - Pachymetry (after IOP measurement)
 - Ophthalmoscopy with pupil dilation (after IOP measurement)
 - Gonioscopy
 - Visual field
- Determine if the subject meets eligibility criteria.
- If the subject meets eligibility criteria and is still willing to continue the study, discontinue any current IOP-lowering medications if any according to the following schedule (up to +7 days as a window is allowed):
 - Miotics: 7 days
 - Oral/topical Carbonic Anhydrase Inhibitors (CAIs): 7 days
 - Alpha agonists: 14 days
 - Alpha/beta agonists: 14 days
 - Alpha antagonists (α 1 blocker): 28 days
 - Beta antagonists (β blocker, including $\alpha\beta$ blockers): 28 days
 - Prostaglandin Analogs (PGA): 28 days
 - Rho kinase inhibitor: 28 days

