8.1. Subject Inclusion Criteria for ADULT Subjects

Inclusion Criteria Specific for ADULT Subjects:

At Visit 1 (Screening), the subjects must meet all of the following inclusion criteria:

1. Provide signed written informed consent on the Institutional Review Board (IRB)/Ethics Committee (EC) approved Informed Consent Form (ICF).
2. Be 18 years of age or older on the date of signing the ICF and be able and willing to comply with all treatment and follow-up study procedures.
3. If a subject is a female of childbearing potential (i.e., not post-menopausal [within 12 months since the last menses] or not surgically sterile [less than 6 months from date of surgery]), she must have a negative urine pregnancy test and must use at least one of the following acceptable contraceptive methods during the study (as well as for 4 weeks following last dose in study).
 - Abstinence
 - Hormonal contraceptive method (including oral or transdermal contraceptives, injectable progesterone, progestin subdermal implants, progesterone-releasing intrauterine devices [IUDs]) initiated at least 28 days prior
 - Placement of a copper-containing IUD
 - Condom with spermicidal foam/gel/film/cream/suppository
 - Vasectomized male partner (surgery at least 6 months prior)

Male subjects capable of fathering children should use/ practice an acceptable contraceptive method, such as abstinence, condom or vasectomy (surgery at least 6 months prior) or other contraceptive method deemed adequate by the investigator throughout the course of the study (as well as for 12 weeks following last dose in study).

4. Must have a diagnosis of OAG (including Pigmentary Glaucoma or Pseudoexfoliative Glaucoma) or OHT in both eyes, or one eye with OAG and the other with OHT.
5. BCVA of +0.60 logMAR (Snellen equivalent 20/80) or better in each eye.
6. Central corneal thickness $\geq 480 \mu\text{m}$ and $\leq 600 \mu\text{m}$ in each eye.
7. Anterior chamber angle grade ≥ 2 (Shaffer scale) in each eye.

In addition to continuing to meet inclusion criterion 5 (BCVA), the subject must meet the following criteria at Visit 2 (Baseline, Day 1):

8. Completed the required wait/washout period.

9. At all time points of IOP measurements (08:00, 10:00 and 16:00) at Visit 2 (Baseline, Day 1), have IOP of ≥ 22 mmHg in at least one eye (the same eye), and ≤ 34 mmHg in both eyes.

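### Protocol 21.3.2 exempts a recently sterilized woman from pregnancy testing, while adult inclusion criterion 3 counts her as of childbearing potential for 6 months after surgery and requires a negative test

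*Protocol*

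**What the plan says.** Adult inclusion criterion 3, in the synopsis and in Protocol Section 8.1, places in the childbearing-potential group a woman who is "not surgically sterile [less than 6 months from date of surgery". For anyone in that group, "she must have a negative urine pregnancy test". The list that contains criterion 3 opens with "At Visit 1 (Screening), the subjects must meet all of the following inclusion criteria".

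Protocol Section 21.3.2 sets out the test procedure. It lists the visits, ending with "Visit 8 Study Exit/Early Termination for all females of childbearing potential", and then gives its own definition: "A female is considered of childbearing potential unless she is post-menopausal (at least 12 months since last menses occurred), is without a uterus". In full, the surgical exemption in that sentence covers a woman who "is without a uterus or without both ovaries, or has had a bilateral tubal ligation". It attaches no interval to any of these operations. Section 21.3 states that the appendix covers adults as well as children.

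The Visit 1 instruction in Section 7.4.1 reads "Obtain urine and perform urine pregnancy test, if the subject is a female of child-bearing potential". Footnote c to Table 3 uses the same term. Neither defines it.

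**The concern.** A site has two places to look. The eligibility list says that a recently sterilized woman must be tested before she can enter. The procedure appendix says that she is outside the tested group. Staff who use the appendix as their working instruction would skip a test that an inclusion criterion demands, and the sponsor's own text would have caused the deviation.

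Two consequences follow. The first is an eligibility deviation: SAP Section 7.4 has a category for inclusion/exclusion criteria, and Protocol Section 8.5 gives failure to meet eligibility as an example of a deviation for which a subject may be discontinued. The second is a small safety gap in a trial where, as Protocol Section 12.1.3 acknowledges, controlled data on the product in human pregnancy are lacking.

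**Working it through.** No arithmetic applies. The check is to set the two definitions side by side, run one case through both, and look for text that reconciles them.

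| Element | Adult criterion 3 (synopsis, 8.1) | Section 21.3.2 |
|---|---|---|
| Menopause | Exempt from 12 months after last menses | Same |
| Tubal ligation | Exempt only from 6 months after surgery | Exempt at once |
| Hysterectomy or bilateral oophorectomy | Exempt only from 6 months after surgery | Exempt at once |
| Consequence if not exempt | Negative urine test and contraception | Urine test at the listed visits |

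Criterion 3 does not name operations. It speaks of surgical sterility, and bilateral tubal ligation is a sterilizing operation, so it falls under the 6-month limit.

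Test case: a premenopausal adult three months after bilateral tubal ligation.

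- Under criterion 3 she is of childbearing potential and needs a negative test at Visit 1.
- Under 21.3.2 she is not of childbearing potential and is tested at no visit.
- From 6 months after surgery the two definitions agree.

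Search for reconciling text:

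- Section 7.4.1 and footnote c to Table 3 leave the term undefined.
- The summary of changes in Section 21.6 does not mention it. Both texts are current, so this is not a difference from superseded wording.
- The 6-month interval looks deliberate. Criterion 3 uses the same interval for vasectomy, both in a partner and in male subjects. Tubal ligation is also absent from its list of accepted contraceptive methods.

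Visit 2: Section 7.1 places the final eligibility decision there, Section 7.4.3 asks for a last eligibility review after the 16:00 pressure reading and schedules a pregnancy test, and Table 3 marks the eligibility criteria at both Visit 1 and Visit 2. It is therefore arguable that criterion 3's test requirement also applies at Visit 2.

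**The case against.** The strongest reply is that the failure is unlikely. Criterion 3 puts its definition and its test requirement in one sentence, and that sentence appears twice. Section 8 requires all criteria to be met, and Section 7.4.1 has the site determine eligibility at Visit 1, so nobody can be enrolled properly without reading criterion 3. Section 21.3.2 does not forbid the test, and a site that knows both texts complies simply by testing. This stands, and it limits the consequence. It does not remove the contradiction, because the text that tells staff whom to test gives the wrong answer for this woman.

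The second reply is that other safeguards remain. Pregnancy is an exclusion at Visits 1 and 2 (Section 8.2), criterion 3 still obliges this woman to use contraception, and pregnancy is both a reason for withdrawal (Section 8.5) and an event of special interest (Section 12.1.3). This also stands.

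A reader might infer more than the documents support:

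- *That criterion 3 binds at Visit 1 only.* The sentence "In addition to continuing to meet inclusion criterion 5 (BCVA), the subject must meet the following criteria at Visit 2 (Baseline, Day 1" invites this reading. The Visit 2 eligibility provisions in Sections 7.1 and 7.4.3 and in Table 3 make it contestable.
- *That a definite number of later tests would be lost.* The documents do not say which definition governs tests after eligibility is settled. Criterion 3's contraception duty runs through the study and for 4 weeks after the last dose, which favors its definition, but that does not expressly decide who is tested. Any count would rest on an assumption.
- *That 21.3.2 wrongly demands tests in pre-menarchal girls.* Pediatric criterion 4 offers no rival definition, so no two texts conflict there. Treating a young child as of childbearing potential also strains the ordinary meaning of the term.

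**Conclusion.** The inconsistency is real and minor. Following 21.3.2 as written omits a test that an adult inclusion criterion requires at Visit 1, and arguably at the Visit 2 eligibility review, in a woman less than 6 months past sterilizing surgery. The practical case is recent tubal ligation, since a pregnancy test after hysterectomy adds nothing.

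The number affected is probably small, but the documents give no figure for recently sterilized women. Efficacy and power are unaffected. The Per-Protocol Set should be too, because SAP Section 5.4 excludes subjects only for deviations that might affect the primary efficacy analysis.

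The conclusion rests on two readings: that surgical sterility in criterion 3 includes tubal ligation, and that being post-menopausal or being surgically sterile is each enough to take a woman out of the childbearing-potential group.

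**What to change.** In Section 21.3.2, replace the definition for adult subjects with: *childbearing potential as defined in adult inclusion criterion 3 (surgical sterility counts only from 6 months after surgery)*. State that this definition governs every scheduled and early-termination pregnancy test in adults. Criterion 3 itself need not change: the aim is to bring the procedure into line with the eligibility rule already adopted, neither narrowing the 6-month interval to particular operations nor rewriting the pediatric criteria.

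The cost is a wording amendment and a few extra urine tests. Section 17.1 requires ethics re-approval of amendments, so the change is best bundled with the next one.
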